9.5.4 Pregnancy Test

Screening for urine pregnancy, using pregnancy strip, will be performed on Day 1 and on Day 29 before vaccination for WoCBP only. It is not required for postmenopausal or surgically sterilized women.

A positive urine pregnancy test should be confirmed by a serum test. Pregnancy tests may be performed more frequently per request of Institutional Review Board (IRB)/Independent Ethics Committee (IEC) or if required by local regulations.

9.5.5 Self-Evaluation/Reporting (Solicited/Unsolicited Symptoms)

9.5.5.1 Solicited Symptoms

Information of solicited symptoms and body temperature will be collected by the subjects in the provided e-diary cards during a 7-day follow-up period after each vaccination (i.e. day of vaccination and 6 subsequent days), and reported by the investigator team. Meanwhile, skin allergic reaction should be monitored for 14 days via e diary. The subject should complete the assessments in the e-diary every evening.

Local reaction, skin allergic reaction, and systemic event are the one whose nature or intensity is consistent with the expected AEs described and listed below.

Table 9-1 Grading for local reaction

Local Reaction	Mild (Grade 1)	Moderate (Grade 2)	Severe (Grade 3)	Potentially Life Threatening (Grade 4)
Pain at injection site	Does not interfere with activity	Interferes with activity	Prevents daily activity	Emergency room visit or hospitalization for severe pain
Itching at injection site	Does not interfere with activity	Interferes with activity	Prevents daily activity	Emergency room visit or hospitalization for severe symptoms
Redness	>2.0 to 5.0 cm (5 to 10 measuring device units)	>5.0 to 10.0 cm (11 to 20 measuring device units)	>10 cm (≥21 measuring device units)	Necrosis or exfoliative dermatitis
Swelling	>2.0 to 5.0 cm (5 to 10 measuring device units)	>5.0 to 10.0 cm (11 to 20 measuring device units)	>10 cm (≥21 measuring device units)	Necrosis or exfoliative dermatitis

Table 9-2 Grading for allergic skin reaction

Local Reaction	Mild (Grade 1)	Moderate (Grade 2)	Severe (Grade 3)	Potentially Life Threatening (Grade 4)
Skin allergic reaction	Localized urticaria (wheals) with no medical intervention indicated	Localized urticaria with intervention indicated OR Mild angioedema with no medical intervention indicated	Generalized urticarial OR Angioedema with intervention indicated	Anaphylaxis

Table 9-3 Grading for systemic events

Systemic Event	Mild (Grade 1)	Moderate (Grade 2)	Severe (Grade 3)	Potentially Life Threatening (Grade 4)
Subjective fever	Does not interfere with activity	Some interference with activity	Prevents daily routine activity	Emergency room visit or hospitalization for severe symptoms
Chills	Does not interfere with activity	Some interference with activity	Prevents daily routine activity	Emergency room visit or hospitalization for severe chills
Nausea/anorexia	Does not interfere with activity	Some interference with activity	Prevents daily routine activity	Emergency room visit or hospitalization for severe symptoms
Vomiting	1 to 2 times in 24 hours	>2 times in 24 hours	Requires intravenous hydration	Emergency room visit or hospitalization for hypotensive shock
Diarrhea	2 to 3 loose stools in 24 hours	4 to 5 loose stools in 24 hours	6 or more loose stools in 24 hours	Emergency room visit or hospitalization for severe diarrhea
Headache	Does not interfere with activity	Some interference with activity	Prevents daily routine activity	Emergency room visit or hospitalization for severe headache
Fatigue/tiredness	Does not interfere with activity	Some interference with activity	Prevents daily routine activity	Emergency room visit or hospitalization for severe fatigue
Muscle pain	Does not interfere with activity	Some interference with activity	Prevents daily routine activity	Emergency room visit or hospitalization for severe new or

Systemic Event	Mild (Grade 1)	Moderate (Grade 2)	Severe (Grade 3)	Potentially Life Threatening (Grade 4)
				worsened muscle pain
Joint pain	Does not interfere with activity	Some interference with activity	Prevents daily routine activity	Emergency room visit or hospitalization for severe new or worsened joint pain

The axillary temperature will be monitored every evening on day of vaccination and 6 subsequent days. If axillary temperature has been measured for more than one time, only the highest degree level should be recorded in the e-diary card.

Table 9-4 Grading for axillary temperature

	Mild (Grade 1)	Moderate (Grade 2)	Severe (Grade 3)	Potentially Life Threatening (Grade 4)
Fever (°C)	37.3 ~ <38.0	38.0 ~ <38.5	38.5 ~ <39.5	≥39.5, last more than 3 days

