6.2 Primary Endpoint(s)

Immunogenicity Endpoint(s)

- Geometric mean titer (GMT) of SARS-CoV-2 neutralizing antibody on Day 57
- Seroconversion rate (SCR) of SARS-CoV-2 neutralizing antibody on Day 57

Safety Endpoint(s)

- Local reactions for up to 7 days following each dose
- Systemic events for up to 7 days following each dose
- Unsolicited AEs from Day 1 to Day 57
- MAAEs and SAEs from Day 1 to Day 365
- AESIs and ADEs from Day 1 to Day 365

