Before any study-related procedures are performed, voluntary, written, study-specific informed consent will be obtained from the subjects. **Subjects will be screened at Visit 1.** All subjects will have blood sampling for hematology and biochemistry. After checking the eligibility of the subject at Visit 2, the randomization number and adjoining study intervention allocation will be assigned. **Subjects in lot-to-lot consistency and immunogenicity group will have blood drawn for immunogenicity before vaccination.** Unblinded site staff member(s) will dispense/administer 0.5 mL UB-612/placebo into the deltoid muscle of the preferably nondominant arm. Blinded site staff must observe the subject for at least 30 minutes after study vaccine administration for changes in vital signs or any acute anaphylactic reactions. The investigator will provide instructions for reactogenicity e-diary completion and ask the subject to complete the reactogenicity e-diary from

Day 1 to Day 7, skin allergic reaction e-diary from Day 1 to Day 14, with Day 1 being the day of vaccination. Participants will be instructed to contact the site staff or investigator immediately if he or she experiences any of the Grade 3/4 AEs from Day 1 to Day 7 to determine if an unscheduled reactogenicity visit is required. Apart from reactogenicity, allergic skin rash should be monitored for 14 days post vaccination. **Once subject encountered the Grade 3/4 allergic skin rash, site staff should call for detail to evaluate the necessity of unscheduled visit. Investigators could ask for HLA typing survey if he/she concerned about the possibility of hypersensitivity. Of course, IDMC could also request HLA typing once they reviewed the safety data.**

At Visit 3 (Day 29), the 2nd study vaccine administration will be done and subjects will be closely monitored for 30 minutes after vaccination for changes in vital signs or acute anaphylactic reaction. The 7/14-day post-vaccination e-diary will be given to subjects with a suitable instruction. For females of child-bearing potential, a urine pregnancy test will be performed before vaccination and found negative. At Visit 4 (Day 57, 1-month follow-up visit after 2nd vaccination), collect sample for safety and immunogenicity, review the participants' reactogenicity e-diary data and record any unsolicited AE.

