9.5.5.2 Unsolicited Adverse Event

An unsolicited local and general AE or symptoms are the one whose nature or intensity is NOT consistent with the expected AEs described and listed above in this protocol. Information of unsolicited symptoms/AEs will be collected during study period and reported at each visit or safety calls.

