10.5 Safety Evaluation

All safety assessments, including AEs, PEs, VS and clinical laboratory evaluations, where indicated, will be presented using descriptive statistics for each study group of UB-612. Data will be summarized for each study group.

Local Reactions and Systemic Events

Local reactions and systemic events recorded on e-diary will be summarized by the severity grading scales by study groups. Numbers and percentages of subjects experiencing each local reaction/systemic event will be presented for each symptom severity by study groups. Summary tables showing the occurrence of any local reactions and occurrence of any systemic event will also be presented.

Unsolicited Adverse Event

This analysis applies to all unsolicited adverse events occurring during the study, recorded in AE eCRF, with a start date on or after the date of vaccination. Unsolicited AEs occurring during the study will be coded using the most recent version of Medical Dictionary for Regulatory Activities (MedDRA). The adverse events will then be grouped by MedDRA preferred terms into frequency tables according to system organ class.

All reported unsolicited adverse events, as well as adverse events judged by the investigator as at least possibly related to study vaccine, will be summarized according to system organ class and preferred term within system organ class. When an unsolicited adverse event occurs more than once for a subject, the maximal severity and strongest relationship to the study group will be counted.

Separate summaries will be produced for the following categories, such as serious adverse events and unsolicited AEs related to vaccinations will be presented. Data listings of all unsolicited adverse events will be provided by subject.

Physical Examination

All physical examination findings will be listed and summarized by time point and study group. Shift table will be also presented, if appropriate.

Vital Signs

All vital sign findings will be listed and summarized by time point and study group.

Laboratory Evaluations

Laboratory safety data will be analysed descriptively by time point and study group. Shift table for laboratory data will be shown by visit using categorization of laboratory according to local laboratory's normal reference range.

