10.5.1 Analysis of Primary Safety Endpoint(s)

- Local reactions for up to 7 days following each dose

Local reactions for up to 7 days following each dose will be summarized with counts and percentages of participants with the indicated endpoint and the associated Clopper-Pearson 95% CIs by study group and each vaccination. The group comparison will be assessed by Fisher's exact test. Summary of descriptive statistics by age group will be also provided.

- Systemic events for up to 7 days following each dose

Systemic events for up to 7 days following each dose will be summarized with counts and percentages of participants with the indicated endpoint and the associated Clopper-Pearson 95% CIs by study group and each vaccination. The group comparison will be assessed by Fisher's exact test. Summary of descriptive statistics by age group will be also provided.

- Unsolicited AEs from Day 1 to Day 57

Unsolicited AEs will be presented by descriptive summary statistics (counts, percentages, and associated Clopper-Pearson 95% CIs) with system organ class and preferred term for each study group. The group comparison will be assessed by Fisher's exact test. Summary of descriptive statistics by age group will be also provided.

- MAAEs and SAEs from Day 1 to Day 365

MAAEs and SAEs will be summarized by counts, percentages, and associated Clopper-Pearson 95% CIs for each study group. The group comparison will be assessed by Fisher's exact test. Summary of descriptive statistics by age group will be also provided. **Additionally, the AESIs and ADEs occurred after third vaccination for subjects received three vaccinations will be also summarized separately.**

- AESIs and ADEs from Day 1 to Day 365

AESIs and ADEs will be summarized by counts, percentages, and associated Clopper-Pearson 95% CIs for each study group. The group comparison will be assessed by Fisher's exact test. Summary of descriptive statistics by age group will be also provided. **Additionally, the AESIs and ADEs occurred after third vaccination for subjects received three vaccinations will be also summarized separately.**

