10.9 Interim Analysis

Six interim analyses and reports will be performed when (1) adult immunogenicity data (350 evaluable young adults and 154 evaluable elderly subjects) for Day 57 are available; (2) at least half of core group subjects (at least 3500 evaluable subjects) will be completed Day 85 safety follow up, as EUA application dossier; (3) all immunogenicity data for lot-to lot consistency of Day 57 are available, EUA application dossier; (4) 350 evaluable adolescents completed Day 57 safety follow up, as supplementary dossier for EUA; **(5) immunogenicity and safety data for young and elderly adult subjects receiving 3rd vaccination completed Visit 7, which is 14 days after 3rd vaccination; (6) immunogenicity and safety data for adolescent subjects receiving 3rd vaccination completed Visit 7, which is 14 days after 3rd vaccination.**

The first four analyses and reports will be analysed and drafted by the unblinded statistician, reviewed by the IDMC, and submitted to appropriate regulatory authorities for review if as EUA application dossier or supplementary dossier for EUA.

For the evaluation of safety, immunogenicity, and lot-to-lot consistency, the following endpoints will be included in the first four interim analyses.

- Local reactions, systemic events, unsolicited AEs, and SAEs
- Changes of safety laboratory measures
- Changes of vital signs and physical examinations
- Seroconversion rate of SARS-CoV-2 neutralizing antibody and antigen-specific antibody (Anti-S1-RBD) on Day 57
- Geometric mean titer of SARS-CoV-2 neutralizing antibody and antigen-specific antibody (Anti-S1-RBD) on Day 57
- Geometric mean fold increase in SARS-CoV-2 neutralizing antibody and antigen-specific antibody (Anti-S1-RBD) on Day 57
- Lot consistency by the comparisons of the GMT of SARS-CoV-2 neutralizing titers on Day 57 induced by 3 independent UB-612 vaccine clinical materials. The 95% confidence intervals between groups will be within the margin of 0.5 to 2.

For last two interim analyses (i.e., interim analysis (5) and (6)), the analyses demonstrate the immunogenicity and safety data on the adult and adolescent subjects received 3rd dose of UB-612 including (but not limited to) following endpoints.

- **Local reactions, systemic events, unsolicited AEs, and SAEs after 3rd dose of UB-612**
- **Changes of safety laboratory measures**
- **Changes of vital signs and physical examinations pre/post 3rd dose of UB-612**

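### V-205 solicits skin allergic reactions for 14 days but gives them no endpoint or summary of their own, and non-serious Day 8–14 events can fall between the solicited and unsolicited tables

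*Supplement*

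**What the plan says.** All references are to the V-205 protocol unless stated.

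- **Collection.** Section 7.1 sets a "skin allergic reaction e-diary from Day 1 to Day 14, with Day 1 being the day of vaccination". Section 9.5.5.1 repeats the 14 days: "Meanwhile, skin allergic reaction should be monitored for 14 days via e diary". Table 9-2 grades the reaction from localized urticaria (Grade 1) to anaphylaxis (Grade 4). The text above the tables lists three kinds of solicited event: "Local reaction, skin allergic reaction, and systemic event are the one whose nature or intensity is consistent with the expected AEs described and listed below".
- **Endpoints.** Section 6.2 has "Local reactions for up to 7 days following each dose", the same for systemic events, unsolicited AEs to Day 57, and MAAEs, SAEs, AESIs and ADEs to Day 365. Section 6.6 mirrors this for adolescents.
- **Analysis.** Section 10.5: "Local reactions and systemic events recorded on e-diary will be summarized by the severity grading scales by study groups". Section 10.5.1: "Local reactions for up to 7 days following each dose will be summarized with counts and percentages". The tables by system organ class and preferred term cover unsolicited AEs only.
- **Definition.** Under 9.5.5.2 an unsolicited event is one "whose nature or intensity is NOT consistent with the expected AEs described and listed above".
- **Interim reports.** The AE content of the first four is "Local reactions, systemic events, unsolicited AEs, and SAEs" (10.9).

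**The concern.** Allergic skin reaction is the one reactogenicity item for which the sponsor lengthened the diary. It also receives a specific question at the Day 8 and Day 15 calls and possible HLA typing. A reader would expect a randomized, placebo-controlled 14-day rate by grade. The plan names no such result.

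The definition of unsolicited makes matters worse. Because it sorts by type and not by time, a late event of a listed type is too late for the 7-day endpoint and of the wrong type for the unsolicited tables. A mild urticaria on Day 10 is one example; an injection-site reaction or fever on Day 9 is another. Three of the first four interim reports are EUA or supplementary EUA dossiers, so any undercount would reach the regulator.

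**Working it through.** The plan states no figure to reproduce. The check compares windows and traces each route by which an event could be counted.

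**Windows.** Day 1 is the day of vaccination. The local and systemic diary runs Days 1–7 and the skin diary Days 1–14. Days outside the solicited endpoints: 14 − 7 = 7 per dose (Days 8–14).

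**Routes for a skin allergic reaction that starts on Days 8–14:**

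| Route | Open? | Reason |
|---|---|---|
| Local or systemic endpoint (6.2, 10.5.1) | No | Limited to 7 days |
| Unsolicited AE (9.5.5.2, 10.5) | No, read literally | The type is on the solicited list; no time limit is given |
| AESI or ADE (Tables 9-5, 9-6) | No, as listed | Urticaria, angioedema and anaphylaxis are in neither table; Table 9-5 also needs a positive PCR |
| SAE | If serious | Primary endpoint, and on the interim lists |
| MAAE (8.3, 9.5.6.4) | If medically attended | Primary endpoint, but not on the list for the first four interims |

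**How complete is the MAAE route?** It depends on a visit taking place.

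- After dose 1, section 8.1.3 has staff ask about allergic skin reaction on Days 8 and 15 and arrange an unscheduled visit, with no grade threshold. Section 8.1.10 does the same at the call 7 days after dose 3.
- Dose 2 is given on Day 29, so its Days 8–14 are study Days 36–42 (29 + 7 to 29 + 13). The calls on Days 36 and 43 (8.1.5) correspond to Days 8 and 15 after the dose, but they carry no allergic-skin question and no visit instruction.
- Section 7.1 has staff telephone about a Grade 3/4 rash to judge whether a visit is needed. It says elsewhere that contact is made whatever the severity. Contact alone does not make an event an MAAE.

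The clearest gap is therefore a Grade 1–2 reaction on Days 8–14 after dose 2.

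**Scale, for illustration.** Adult vaccinees: 3850 × 6/7 = 3300. Each 1% with such an event: 0.01 × 3300 = 33 subjects.

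**The case against.** A reader might infer that no endpoint, analysis or interim report counts these reactions at all. The documents do not support that.

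- Serious reactions are SAEs, and SAEs are on the interim lists.
- Reactions verified at an unscheduled visit are MAAEs, a primary safety endpoint with exact confidence intervals and Fisher's test by study group.
- The first column of Table 9-2 is headed as a local reaction. The diary sentence in 10.5 and the list in 10.9 carry no 7-day limit. On that reading, diary entries over all 14 days could enter the descriptive and interim tables.

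These points stand. They show that the text is ambiguous, because 9.5.5.1 lists skin allergic reaction separately from local reaction. They do not supply an endpoint or a named summary.

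It can also be said that late events would in practice be recorded as unsolicited. All AEs go on the CRF (9.5.6.8), and 8.1.3 speaks of other unsolicited allergic reactions. V-122 used the same definition (9.6.4.2), and section 5.5 of V-123 reports that some local reactions there were entered in the AE eCRF as unsolicited. That report attributes this to procedural issues, and such injection site reactions were seen in 6 of 20 subjects in the 10 µg group. The episode shows that the definition does not settle where an event goes.

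Finally, no analysis plan is shown, and 10.1 leaves full detail to it. Table layout can indeed wait for that document. The endpoint list, the definition of unsolicited and the interim contents are set in the protocol.

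**Conclusion.** The point holds in a limited form. A solicited 14-day category has no endpoint or planned summary of its own. As 9.5.5.2 is worded, non-serious events of a listed type that start after the 7-day endpoint window and are not medically attended fall in neither set of tables. For skin allergic reaction that is Days 8–14 after each dose.

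This rests on reading 9.5.5.2 literally and on treating skin allergic reaction as separate from local reaction, as the text of 9.5.5.1 does. How many events are affected is unknown, since no Day 8–14 rate is given; the figure of 33 per 1% is not a forecast. Nor do the documents show that the safety result would in fact look cleaner than the data. The point merits correction, but the trial's validity does not turn on it.

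**What to change.** 1. In 9.5.5.2, define unsolicited by window as well as by term. Any event that starts after its diary window (Day 7; Day 14 for skin allergic reaction) is entered in the AE eCRF and counted as unsolicited, even if its term is on the solicited list.
2. In 10.5, 10.5.1 and 10.9, and for adolescents in 10.7, add a summary of skin allergic reactions to 14 days after each dose, by grade and study group, with Clopper-Pearson intervals.
3. Reconcile 7.1, 8.1.3 and 8.1.5 on how allergic reactions are followed up after each dose. Which clinical rule applies is for the sponsor and investigators to decide.

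Items 1 and 2 cost some wording and one extra table, using data the diary already collects. The reported reaction rate may rise slightly.

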6.2 Primary Endpoints

- Occurrence of adverse reaction within 7 days after vaccination
 - * Adverse reaction is defined as post-vaccination solicited adverse event, and unsolicited adverse event which is related to study vaccine.
- The percentage of subjects with \geq Grade 3 adverse events within 7 days after vaccination

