9.6.4.2 Unsolicited Adverse Event

An unsolicited local and general AE or symptoms are the one whose nature or intensity is NOT consistent with the expected AEs described and listed above in this protocol. Information of unsolicited symptoms/AEs will be collected until 28-day follow-up period after each vaccination (i.e. day of vaccination and 27 subsequent days) and reported at each visit.

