10.4.1 Analysis of Primary Safety Endpoint

- Occurrence of adverse reactions within 7 days after vaccination
All adverse reactions within 7 days after vaccination will be summarized with frequencies and percentages by study vaccine group and each vaccination.
- The percentage of subjects with \geq Grade 3 adverse events within 7 days after vaccination
The subject who has \geq Grade 3 solicited AE or \geq Grade 3 unsolicited AE within 7 days after vaccination will be counted. The number and percentage of counted subjects will be demonstrated by study vaccine group and each vaccination.

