9.6.1 Overall Study Stopping Rules

The following stopping rules are in place for all subjects, based on review of AE data and e-diary reactogenicity data.

1. An SAE that is assessed by the investigator as possibly related, or for which there is no alternative, plausible, attributable cause.
2. A Grade 4 local reaction, systemic adverse event or fever that is assessed as possibly related by the investigator, or for which there is no alternative, plausible, attributable cause.
3. If any 3 subjects vaccinated with UB-612 (at any dose level) report the same or similar* severe (Grade 3) AE (including laboratory abnormalities), assessed as possibly related by the investigator, or for which there is no alternative, plausible, attributable cause.

* defined as same preferred term of current MedDRA

4. If a stopping rule is met, further dosing will be paused and the IDMC will determine whether dosing should resume.
5. If two of the same or similar *SAEs or Grade 4 local or systemic reactions occur, dosing will be suspended and both the IDMC and regulatory authorities will be consulted before resumption of dosing.

* defined as same preferred term of current MedDRA

In the event that a stopping rule is met, the following actions will be taken:

- The stopping rule will PAUSE randomization and administration of study vaccine at all dose levels and all treatment groups.
- The IDMC will review the relevant safety data.

- For all subjects already vaccinated, all other routine study conduct activities, including ongoing data entry, reporting of AEs, electronic diary completion, blood sample collection, and subject follow-up, will continue during the pause.
- Data from placebo recipients will not contribute to the stopping rules.
- Electronic diary data confirmed by the investigator as having been entered in error will not contribute toward a stopping rule.

Should the study be terminated prematurely, the sponsor will provide written notification to all investigators and regulatory authorities specifying the reason(s) for early termination. The investigator must inform the institutional review board (IRB)/independent ethics committees (IEC) promptly and provide the reason(s) for the termination. Previously dosed subjects will be assessed through all planned study safety visits.

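### Read as printed, the fever scale in all three protocols gives no grade to 39.5 °C or more lasting 3 days or less, so V-122 and V-123 may miss such a subject in their Grade 3 or higher primary endpoint, and V-205's severity tables and fever-grade rules do not place it.

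*Supplement*

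**What the plan says.** The fever scale is in V-122 Table 9-3 (section 9.6.4.1), V-123 Table 9-3 (section 9.5.4.1) and V-205 Table 9-4 (section 9.5.5.1). The bands are identical: Grade 1 from 37.3 to below 38.0 °C, Grade 2 from 38.0 to below 38.5 °C, Grade 3 from 38.5 to below 39.5 °C, and Grade 4 "≥39.5, last more than 3 days". Only Grade 4 carries a duration. No footnote covers 39.5 °C or more for a shorter time.

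Axillary temperature is taken every evening on the vaccination day and the 6 days after it. If it is measured more than once, "only the highest degree level should be recorded in the e-diary card".

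The grade is then used as follows:

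- **V-122 and V-123, section 6.2:** a primary safety endpoint is the percentage of subjects with at least "Grade 3 adverse events within 7 days after vaccination". Under V-122 section 10.4.1 the count takes solicited events of that severity, and any subject with at least a "Grade 3 unsolicited AE within 7 days after vaccination will be counted". V-123 section 10.4.1 says the same.
- **V-205, section 6.2:** the corresponding primary endpoint is "Systemic events for up to 7 days following each dose", with no grade threshold. Section 10.5 adds: "Numbers and percentages of subjects experiencing each local reaction/systemic event will be presented for each symptom severity by study groups".
- **V-205, section 9.6.1:** one stopping rule is "A Grade 4 local reaction, systemic adverse event or fever that is assessed as possibly related by the investigator". Sections 7.1 and 8.3 tie telephone contact to Grade 3 fever and a site visit to suspected Grade 4 fever.

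**The concern.** A severity scale should not lose a case as the measurement rises. Here the Grade 3 band is closed at the top, and the next band opens only if a second condition, duration, is also met. Between them lies a region of high temperature and short duration with no grade, although it is more extreme than readings that are Grade 3.

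This matters because the grade, not the temperature, is what gets counted. In V-122 and V-123 it decides whether a subject enters a primary endpoint in groups of 20. In V-205 it decides which row of the severity tables the subject occupies, and those tables feed the interim reports intended for emergency use authorization. Passages on sentinel expansion, second-dose eligibility, subject contact and stopping also refer to Grade 3 or Grade 4 reactions or fever, so they inherit the ambiguity.

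**Working it through.** No sample size or power figure is at issue. The check is to apply the printed scale to every combination of temperature and duration, then trace where the grade is used.

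**Step 1. Literal reading: Grade 4 needs 39.5 °C or more and more than 3 days.** With one evening value per day over 7 days, more than 3 days means 4 or more evenings.

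| Temperature (°C) | 1 to 3 evenings | 4 to 7 evenings |
|---|---|---|
| 38.4 | Grade 2 | Grade 2 |
| 38.5 | Grade 3 | Grade 3 |
| 39.4 | Grade 3 | Grade 3 |
| 39.5 | none | Grade 4 |
| 40.0 | none | Grade 4 |
| 41.0 | none | Grade 4 |

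The result is the same in all three protocols.

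**Step 2. Alternative reading: Grade 4 is 39.5 °C or more, or any fever lasting more than 3 days.** Every value of 39.5 °C or more is now Grade 4, so the gap closes. But 37.4 °C on four evenings is Grade 1 by temperature and Grade 4 by duration, and the same overlap arises for Grades 2 and 3. The note that the higher classification prevails (V-122 and V-123, Table 9-1) covers induration, swelling, rash and redness, not fever. Neither reading gives each fever one grade.

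**Step 3. Where a Grade 3 or higher count is a primary endpoint.** V-122: yes. V-123: yes. V-205: no; its primary safety endpoints are local reactions, systemic events, unsolicited adverse events, MAAEs and SAEs, and AESIs and ADEs, all without a grade threshold.

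**Step 4. Size in V-122 and V-123.** One missed subject in a group of 20 is 1/20 = 5 percentage points. For scale, the Phase I summary in V-123 section 5.5 reports Grade 3 or higher events after the first dose in 2 subjects (10.0%) at 10 µg, 1 subject (5.0%) at 30 µg and none at 100 µg.

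The documents give no incidence of short high fever. Assuming 0.1% to 0.5% per dose, the chance of at least one such subject is 1 − (1 − p)^n:

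- n = 20: 1 − 0.999^20 = 2.0% to 1 − 0.995^20 = 9.5%
- n = 60: 1 − 0.999^60 = 5.8% to 1 − 0.995^60 = 26.0%

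**Step 5. Size in V-205.** Adults allocated to vaccine: 3850 × 6/7 = 3300. Under the same assumption, 3300 × 0.001 = 3.3 to 3300 × 0.005 = 16.5 subjects per dose would have such a fever. This is an upper bound on those without a place in the severity tables, since some would be graded by another route.

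**The case against.** A reader might infer that every short fever of 39.5 °C or more is lost from a Grade 3 or higher primary count in all three protocols. The documents do not support that.

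- **V-205 has no such endpoint.** An ungraded 39.8 °C can still be counted as a systemic event. V-205 also grades subjective fever separately, by interference with activity (Table 9-3).
- **Another evening may qualify.** A subject with 39.8 °C one evening and 38.9 °C the next has a Grade 3 reading. This helps some subjects only; a one-evening spike need not leave a second reading in the Grade 3 band.
- **The unsolicited route may apply.** V-122 section 9.6.4.2 defines an unsolicited event as "the one whose nature or intensity is NOT consistent with the expected AEs described and listed above in this protocol". Such events would be graded by CTCAE, and the V-122 and V-123 primary counts include unsolicited events. But CTCAE grading is stated for adverse events other than those in the e-diary, temperature is an e-diary item, and no passage sends fever this way. In V-205 the route would also move the event out of the systemic-event endpoint.
- **The contact rule is softer than the grade.** In V-205 the site visit is triggered by suspected Grade 4 fever, and a first reading of 39.5 °C or more could reasonably be treated as suspected while its duration is unknown. That stands, although the text does not say so. It does not settle the stopping rule or the tables.
- **The SAPs are not shown.** They may contain a derivation rule, so the lack of one in the protocols is not the fault claimed here. The fault is in the printed tables.

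The Phase I summary offers no evidence of a missed fever: its three Grade 3 or higher events within 7 days were all rises in diastolic blood pressure. Nor does it show that none was missed.

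**Conclusion.** The point holds in a limited form. The gap is in all three fever tables on the literal reading, and the only evident alternative exchanges it for an overlap. In V-122 and V-123 a subject with a short high fever may be missed from a primary safety endpoint, at 5 percentage points per subject in a 20-subject group. This is a risk, conditional on no other reading or unsolicited record capturing the subject. In V-205 the effect is on the by-severity tables of solicited systemic events and on the rules that refer to Grade 3 or 4 fever, not on a primary endpoint defined by grade.

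The incidence range is an assumption. The 5-point figure rests only on the planned group size. The conclusion also assumes that the analysis applies the table as printed.

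**What to change.** **For the analysis:** in each SAP, derive Grade 3 or higher fever as any e-diary axillary reading of 38.5 °C or more within the 7 days, regardless of duration. The gap lies between Grade 3 and Grade 4, so this count is right whichever of the two it is given. It needs only the highest reading, which is already collected, and can be applied retrospectively. Report separately the number of subjects with 39.5 °C or more for 3 days or less, so that the reader sees how many the gap affects.

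**For the protocols:** the sponsor should state whether the Grade 4 cell means both conditions or either one. The three tables should then be reworded so that each combination of temperature and duration has exactly one grade. If 'either' is meant, the sponsor must also say how long mild fevers are counted, because the 38.5 °C derivation does not include them.

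**Reconcile** the tables with each other and with the passages that use these grades:

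- V-122 sections 7.1, 7.4.4 and 9.6.7
- V-123 section 9.5.8
- V-205 sections 7.1, 7.4.4.2, 8.3 and 9.6.1

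Which grade applies is a clinical decision for the sponsor, and this review proposes none.

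The cost is one line in each table and one derivation rule in each SAP, with no new data.
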